4. PLANNED ANALYSIS

4.1. SUMMARY OF CHANGES TO THE PLANNED STATISTICAL ANALYSIS DESCRIBED IN THE PROTOCOL

1. Change of the name of analysis set:

The name of the primary efficacy analysis set has been modified. Evaluable Efficacy Analysis Set is now referred as the Intention-to-Treat Efficacy Analysis Set (ITT EAS) to emphasize that inclusion in this analysis set is only based on the presence of measurable disease at baseline (per IERC) and no subject may be excluded from this set based on information collected after study treatment initiation.

Note: The original term might be incorrectly interpreted as excluding subjects based on non-evaluable post-baseline data.

2. Definition of ITT Prior Line of Therapy (ITT PLT) Analysis Set. The SAP introduces the ITT PLT set, which includes all subjects with measurable disease and a prior platinum-based line of treatment in a recurrent/persistent/metastatic disease setting as determined by an Independent Review Committee. The analysis set will be used for secondary analysis of efficacy.

3. Definition of Per Protocol Efficacy Analysis Set (PP EAS): PP EAS is defined as a subset of ITT EAS with exclusion of subjects with major protocol deviations deemed likely to affect the efficacy outcomes; it will be used for sensitivity analysis of efficacy.

4. Removal the secondary endpoint of duration of stable disease specified in the protocol due to its similarity to progression-free survival (another secondary endpoint).

5. Second interim analysis:

The first interim analysis was conducted as specified in the protocol. Then, study protocol prescribed the subsequent interim analysis to be “performed 3 months after approximately 100 subjects have been dosed.” The intended goal of this analysis was to support potential Biologics License Application (BLA) submission under subpart E for accelerated approval. However, due to fast accrual in the final stages of study enrollment and feedback received from FDA, the plans for this analysis were modified: the interim analysis was replaced by the BLA Filing analysis which is to be performed using data of all subjects dosed for safety analysis and all subjects dosed with measurable disease for efficacy analysis to support regulatory filing (see [Section 4.2](#) for planned timing of these analyses).

6. Inclusion of a new secondary endpoint (tumor control rate: TCR) defined as the rate of best overall response with either a confirmed response or stable disease at 6 weeks (see [Section 7.7.5](#)).

4.2. INTERIM ANALYSES AND DATA MONITORING

The Protocol specified that Phase 2 is designed to have at least 2 interim analyses of the primary endpoint and selected secondary efficacy and safety endpoints. No early stopping for efficacy will be performed, as a more complete assessment of safety and durability of responses will be required for evaluation of risks and benefits. Consequently, the overall type I error will not be affected by the interim analyses.

The first pre-specified interim analysis was performed based on the prospectively defined interim analysis SAP, when data were available for approximately 30 subjects treated for at least 3 months. The analysis included, for efficacy, all subjects dosed as of 15 Jul 2019 (N = 44), including N = 42 consecutive subjects with measurable disease at baseline for the primary analysis of efficacy. For safety, interim analysis included all subjects dosed by 16 Oct 2019 (the date of the data cutoff), N = 60 such subjects available at the time of the original analysis (however, it was discovered later during re-analysis of the same cohort, using data cutoff of 27 Mar 2020, that N=61 subjects had been actually dosed by 16 Oct 2019; one subject was not accounted for in the original safety analysis due to delayed data entry; the missing subject was included later in an updated analysis). The analysis was conducted according to a standalone Interim Analysis SAP. A non-binding futility assessment consisted of evaluation of conditional and predicted probability (He *et al 2012*) of excluding the ORR of 5% by the lower limit of the Wilson's confidence interval for observed ORR, if the study continued enrollment to 100 and 150 patients.

The second pre-specified analysis was originally planned 3 months after approximately 100 subjects have been dosed and was to include, as the primary analysis of safety and efficacy, all subjects in the evaluable efficacy analysis set among the first approximately 100 subjects dosed. The goal of this analysis was to support regulatory BLA filing. However, due to fast accrual at the final stage of enrollment (consequently short follow-up at the time of the planned analysis) and in consideration of feedback received from FDA, the plans for this analysis were modified: the analysis was replaced by BLA Filing analysis below described below.

BLA Filing analysis is planned to be performed on all subjects dosed using data cutoff of 11 Feb 2021, for at least 12-month median follow-up duration (counting from time of the first dose to data cutoff date) and 6-month follow-up on confirmed objective responses (counting from the start of the last objective response to data cutoff date). All subjects dosed will be used in safety analysis and all subjects dosed with measurable disease at baseline (per IERC) will be used for efficacy analysis.

4.3. FINAL ANALYSIS AND REPORTING

The final analysis will be performed after study completion and it will supplement the BLA Filing analysis.

All final planned analyses per protocol and this analysis plan must be performed after either locking records for relevant subjects or visits included in the analysis or the full database lock. See [Section 7](#) for discussion of requirements for data freeze, locking, and source data verification in the context of the COVID-19 pandemic.

5. DEFINITIONS AND CONVENTIONS FOR DATA HANDLING

5.1. DEFINITION OF BASELINE

For all evaluations, unless otherwise noted, baseline is defined as the most recent non-missing measurement prior to the first administration of study drug.

5.2. DEFINITION OF STUDY DAYS

Unless otherwise noted, study days of an evaluation are defined as the number of days relative to the first dose date which is designated as Day 1, and the preceding day is Day -1, the day before that is Day -2, etc.

Study days are calculated as

- (Date of assessment – first dose date + 1) for assessments on/after first dose date
- (Date of assessment – first dose date) for assessments before first dose date

5.3. DEFINITION OF ON-TREATMENT PERIOD

On-treatment period is defined as the time from the first dose of study treatment until the end of treatment safety follow-up (4 weeks \pm 7 days from the last dose of study drug, i.e., until 35 days from the last dose) or end of study, whichever occurs first.

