#### **7.1.8. Predefined Potential AEs of Special Interest for Safety Monitoring**

Selected non-serious and SAEs defined below are considered AESIs and must be recorded as such on the Adverse Event case report forms/worksheets and reported within 24 hours to the Sponsor either by electronic media or paper. Sponsor Contact information can be found in the Investigator Trial File Binder (or equivalent).

Events of clinical interest for this trial include:

- Infusion-related reactions.
- An elevated AST or ALT lab value that is greater than or equal to 3X the upper limit of normal and an elevated total bilirubin lab value that is greater than or equal to 2X the upper limit of normal and, at the same time, an alkaline phosphatase lab value that is less than 2X the upper limit of normal, as determined by way of protocol-specified laboratory testing or unscheduled laboratory testing.

Note: These criteria are based upon available regulatory guidance documents. The purpose of the criteria is to specify a threshold of abnormal hepatic tests that may require an additional evaluation for an underlying etiology. The trial site guidance for assessment and follow up of these criteria can be found in [Section 5.6.4](#).

- Any AE that is reasonably suspected to be immune-mediated (ie, an irAE).

AESIs (both non-serious and serious AEs) identified in this guidance document from the date of first dose through 90 days following cessation of treatment, or 30 days after the initiation of a new anticancer therapy, whichever is earlier, need to be reported to the SPONSOR within 24 hours of the event, regardless of attribution to study treatment, consistent with standard SAE reporting guidelines and either by electronic media or paper.

Subjects should be assessed for possible AESIs prior to each dose. Lab results should be evaluated and subjects should be asked for signs and symptoms suggestive of an immune-related event. Subjects who develop an AE thought to be immune-related should have additional testing to rule out other etiologic causes. If lab results or symptoms indicate a possible irAE, then additional testing should be performed to rule out other etiologic causes. If no other cause is found, then it is assumed to be immune-related.

Any infusion reaction, regardless of Grade, must be reported in an expeditious manner and will be considered an AESI. The reporting of AESI is described in [Section 7.2.2](#).

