## **8.3.4. Safety Analyses**

The extent of exposure to AGEN2034 will be characterized by duration (weeks), number of administrations, cumulative dose (mg/kg), dose intensity (mg/kg/week), relative dose intensity (actual dose given/planned dose), number of dose reductions, and number of dose delays.

Safety analyses will be performed on the safety analysis set. Safety endpoints will be summarized by dose cohort in each phase.

Safety assessments will be based on incidence of AEs, including AESIs, ADRs, immunogenicity, and changes in vital signs (including body weight), ECG, and laboratory values (hematology and serum chemistry).

The on-treatment period is defined as time from first dose of study treatment to last dose of study drug plus 30 days, or the earliest date of new anticancer therapy minus 1 day, whichever occurs first.

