#### **8.3.4.1. Adverse Events**

Adverse events will be coded according to Medical Dictionary for Regulatory Activities (MedDRA) version 21.0. Severity of AEs will be graded using CTCAE (version 4.03) toxicity grading scale whenever possible.

Treatment-emergent AEs are AEs with onset dates during the on-treatment period, or the worsening of an event during the on-treatment period. Incidence of TEAEs, regardless of attribution, and AEs defined as related to AGEN2034 will be summarized by system organ class and preferred term, and described in terms of severity and relationship to AGEN2034.

Analysis of AES will be performed for events that are considered as treatment emergent. Adverse events leading to death or discontinuation of trial treatment, events with CTCAE Grade 3 or higher, study drug-related events, and SAEs will be summarized.

Indications of dose-related ADRs will also be examined.

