5.4. DEFINITION OF AN EXTENDED ON-TREATMENT PERIOD

Extended on-treatment period (follow-up) is defined as the time from the first dose of study treatment through 90 days after the last dose of study treatment or end of study, whichever occurs first. This is used for reporting immune-related AEs and also as a sensitivity analysis for reporting all treatment emergent adverse events.

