7.6.2. Adverse Events

Adverse events (AEs) will be coded using MedDRA v22.1 or later and will be classified by SOC and PT.

Severity of AEs will be assessed by investigators according to NCI-CTCAE v4.03, and AEs will be classified by the investigator as either related or not related to study drug

Pre-existing conditions are those that started before and continued after signing of informed consent. Prior AEs (non-treatment emergent) are those occurring after the subject signed the informed consent and before the administration of the first dose of study treatment. Immune-related AEs will be evaluated in the extended on-treatment period to account for late toxicities. A separate listing will be provided for AEs incurred after on-treatment period.

TEAEs are AEs with onset during or after administration of first dose, or the worsening of a pre-existing condition during the on-treatment period. Immune-related AEs will be considered TEAEs during the extended on-treatment period. In a sensitivity analysis, TEAEs will be defined as AEs with onset during or after administration of first dose, or the worsening of a pre-existing condition during the extended on-treatment period. A separate listing will be provided of all AEs with onset date, or worsening date between end of “On-treatment period” (35 days) and end of “Extended on-treatment period” (90 days).

Any missing onset date, causality, or severity must be queried for resolution. Unresolved / missing causality and severity will be handled according to the following rules:

- An unresolved causality will be considered treatment-related
- An unresolved severity will be identified as an unknown severity

AEs with partial dates will be considered TEAEs unless the AE can unequivocally be determined as not treatment emergent.

The following AEs are considered as AEs of special interest (AESIs):

- Infusion-related reactions per definition in NCI-CTCAE v4.03 specification (*per investigator assessment*)
- Lab-based hepatic toxicity: An elevated aspartate transaminase (AST) or alanine transaminase (ALT) lab value \geq to $3 \times$ upper limit of normal (ULN) with a corresponding elevated total bilirubin value $\geq 2 \times$ ULN, at the same time, an alkaline phosphatase lab value $< 2 \times$ ULN, as determined by way of protocol-specified laboratory testing or unscheduled laboratory testing
- Any AE suspected to be immune-mediated (i.e. an irAE) by the investigator

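### SAP section 5.3 drops the protocol's cut of the on-treatment period at new anticancer therapy and section 5.4 adds a 90-day window without one, so some irAEs, other AESIs, related SAEs and deaths on the next therapy could be counted against balstilimab

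*SAP*

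**What the plan says.** Protocol section 8.3.4 starts the on-treatment period at the first dose and runs it "to last dose of study drug plus 30 days, or the earliest date of new anticancer therapy minus 1 day", taking the earlier of the two dates. Protocol section 8.3.4.1 ties treatment emergence to it: "Treatment-emergent AEs are AEs with onset dates during the on-treatment period".

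SAP section 5.3 builds its window on the safety follow-up visit at 4 weeks with a 7-day allowance, and states the end as "i.e., until 35 days from the last dose) or end of study, whichever occurs first". SAP section 5.4 adds an extended period "through 90 days after the last dose of study treatment or end of study, whichever occurs first". That window is used for irAEs and for a sensitivity analysis of all TEAEs. Neither section mentions new anticancer therapy.

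SAP section 7.6.2 adds no exclusion: "TEAEs are AEs with onset during or after administration of first dose, or the worsening of a pre-existing condition during the on-treatment period". It treats irAEs as TEAEs throughout the extended period, evaluates the immune-mediated clusters in that period, and splits deaths between the treatment period and survival follow-up.

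Two protocol rules limit which events reach the database. Section 7.2.1 closes general AE reporting at 90 days or at new anticancer treatment. Section 7.1.8 has AESIs, which include suspected irAEs, reported "through 90 days following cessation of treatment, or 30 days after the initiation of a new anticancer therapy, whichever is earlier", whatever the attribution.

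SAP section 4.1 lists six changes from the protocol, including the renaming of an analysis set. The changed on-treatment period is not among them.

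**The concern.** The protocol's cut at new therapy keeps toxicity of the next drug out of the balstilimab tables. The SAP removes the cut from the main window, lengthens that window from 30 to 35 days, and adds a 90-day window without a cut, all without declaring it. The SAP does stop or censor at new anticancer therapy in its efficacy rules (sections 7.7.1, 7.7.3 and 7.7.9), so the omission on the safety side looks unintended.

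TEAE frequency is a secondary endpoint, and the safety tables support the BLA Filing analysis. An event that arose on the next therapy could be tabulated as a balstilimab TEAE or irAE, fall into an immune-mediated cluster, or be counted as an on-treatment death. The clusters are defined by preferred term, without regard to attribution. They include diarrhoea, rash, stomatitis and pancytopenia, which do not by themselves identify the causative drug.

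**Working it through.** **Plan's own figure.** SAP 5.3: 4 × 7 + 7 = 35 days, which reproduces. The protocol's fixed end is 30 days, so the main windows differ by 35 − 30 = 5 days even for a subject who never switches.

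**Does end of study supply the missing cut?** No. Under protocol sections 6.3.4.1 and 6.3.4.2, a Phase 2 subject who starts a new therapy still has the 3-month post-treatment visit and then survival follow-up. Starting a new therapy therefore does not end the study for that subject.

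**Window ends.** Let *s* be the day after the last dose on which new therapy starts. The documents give no switch dates, so *s* is an assumption and is shown over a range.

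- Protocol 8.3.4 window ends on day min(30, *s* − 1).
- SAP 5.3 window ends on day 35, and SAP 5.4 on day 90, whatever *s* is.
- Days on the next therapy inside a SAP window = max(0, end − *s* + 1).
- AESI reporting (protocol 7.1.8) ends on day min(90, *s* + 30).
- AESI-reportable days on the next therapy inside the 90-day window = min(90, *s* + 30) − *s* + 1.

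| *s* (assumed) | Protocol end | Next-therapy days in 35-day window | Next-therapy days in 90-day window | AESI reporting end | AESI-reportable next-therapy days |
|---|---|---|---|---|---|
| 14 | 13 | 22 | 77 | 44 | 31 |
| 28 | 27 | 8 | 63 | 58 | 31 |
| 42 | 30 | 0 | 49 | 72 | 31 |
| 60 | 30 | 0 | 31 | 90 | 31 |
| 89 | 30 | 0 | 2 | 90 | 2 |

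The 31 counts both end days, so it is about 30. Under the protocol window the number of next-therapy days is 0 in every row. Restoring the cut in SAP 5.3 ends that window at min(35, *s* − 1), or min(30, *s* − 1), and again leaves 0.

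**Which events can fall in those days?**

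- *Ordinary AEs:* mostly none, because reporting stops at new anticancer treatment (protocol 7.2.1; Table 13, footnote 5).
- *AESIs including irAEs:* reportable for up to 30 days after the switch under protocol 7.1.8.
- *SAEs suspected to be related to trial treatment:* no time limit on reporting (protocol 7.2.1).
- *Deaths:* followed beyond the switch. A death on the next therapy within 35 days of the last dose is on-treatment under SAP 5.3 but not under protocol 8.3.4.

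**The case against.** The strongest reply is that collection already does the work of the cut. General AE reporting closes at new anticancer treatment, and a Safety Follow-up Visit must precede any new therapy started within 4 weeks (protocol 6.4.1.9.1). This stands for ordinary AEs. A reader might infer that chemotherapy toxicity at large will be tabulated as balstilimab TEAEs, and the documents do not support that. The visit rule does not help further, because SAP 5.3 fixes the end by day count and not at the visit.

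Even the AESI route is not settled. Protocol 7.2 describes AESIs as a subset of AEs in the 7.2.1 reporting period, which closes at new therapy, while 7.1.8 runs 30 days past it. The exposure rests on 7.1.8, and these sections need reconciling.

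The irAE tables use investigator-reported irAEs, after efforts to rule out other causes, and include a breakdown by relationship to study drug. Events between the ends of the two windows also get their own listing. So next-therapy events could be counted, not will be, and part of the effect can be seen in the output. The error also runs in the conservative direction for safety, since it adds events to balstilimab. That limits the harm, but it does not make the attribution correct.

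A reader might also infer that SAP 5.4 deleted a protocol cut and should have a hard one put back. The protocol's statistical section has no 90-day on-treatment window, so there was none to delete. Section 5.4 exists to capture late toxicity, and a hard cut would remove genuine delayed balstilimab irAEs.

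Finally, the opening of protocol section 8 lets the SAP modify the plan. The objection is therefore to an undeclared change, not a forbidden one.

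**Conclusion.** The point holds in a limited form. SAP 5.3 departs from protocol 8.3.4 on both the day count and the new-therapy cut, SAP 5.4 adds an uncut window, and SAP 4.1 declares neither. The practical exposure is confined to AESIs including irAEs, related SAEs, and deaths classed as on-treatment.

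Per switching subject, this is 22, 8 or 0 next-therapy days in the 35-day window for an assumed switch on day 14, 28 or 60. About 30 AESI-reportable next-therapy days fall in the 90-day window in each of those cases. These figures assume that protocol 7.1.8 governs AESI collection and that end of study does not come first. They are lengths of time at risk. With no switch dates and no count of subjects who switch, the documents do not support any estimate of how many events would be misattributed or what share of the tables they would make up. The change is worth making because it is cheap and decides which events and deaths count as on-treatment in a filing analysis.

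**What to change.** 1. **SAP 5.3:** add *or the day before the first dose of new anticancer therapy, whichever is earliest*.
2. **Protocol 8.3.4 and SAP 5.3:** use one day count, 30 or 35, in both.
3. **SAP 5.4:** keep the 90-day window. Flag events with onset on or after the start of new anticancer therapy, and report the irAE and immune-mediated cluster tables with and without them.
4. **Protocol 7.1.8, 7.2 and 7.2.1:** reconcile when AESI reporting ends after a switch.
5. **SAP 4.1:** list the changed main window and the added extended window.

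The cost is wording plus one extra set of irAE and cluster tables. No new data are needed, since the SAP already uses the new-therapy start date for efficacy censoring.

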5.4. DEFINITION OF AN EXTENDED ON-TREATMENT PERIOD

Extended on-treatment period (follow-up) is defined as the time from the first dose of study treatment through 90 days after the last dose of study treatment or end of study, whichever occurs first. This is used for reporting immune-related AEs and also as a sensitivity analysis for reporting all treatment emergent adverse events.

5.5. ANALYSIS VISIT WINDOW

Data will be analyzed by scheduled visits, where appropriate. Data collected out of the prescribed timing window will be analyzed as scheduled (i.e., at intended visits). Data that are collected from an unscheduled visit will not be included in the by-visit summary tables but will be presented in the listings. However, data collected at an unscheduled visit will also be considered for toxicity grading, in particular, for laboratory assessments. Additionally, both unscheduled and out of window imaging assessments will be included in efficacy analysis.

5.6. HANDLING OF PARTIAL DATES FOR ADVERSE EVENTS

When determining TEAEs, partial dates will be handled as follows.

- If the day of the month is missing, the onset day will be set to the first day of the month unless it is the same month and year as study treatment. In this case, the onset date will be assumed to be the first dose date of treatment.

- If the onset day and month are both missing, the day and month will be assumed to be 1 January, unless the event occurred in the same year as the study treatment. In this case, the event onset will be coded to the first dose date of treatment to conservatively report the event as treatment emergent.
- A missing onset date will be coded as the first dose date of treatment. If the resulting onset date is after a reported date of resolution, the onset date will be set equal to the date of resolution.
- A partially missing resolution date will be conservatively imputed as the latest date in the range of missing date element(s) (for example 2020-10-31 if the date is 2020-10-UNK), date of last dose + 90 days, day of study discontinuation, or death, whichever comes first.

Data listings will present the partial date as recorded in the electronic case report form (eCRF).

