### 7.2.1. Definition of the Adverse Event Reporting Period

The AE reporting period for safety surveillance begins when the subject provides written consent and continues until either 90 days after the last dose of study drug or the start of new anticancer treatment, whichever comes first. Following the End-of-Treatment Safety Follow-up Visit, only treatment-related AEs will be documented through the Treatment Follow-up Period of up to 12 months after the last dose of study drug or until disease progression and/or initiation of a new line of therapy, whichever comes first.

Any SAE suspected to be related to trial treatment must be reported whenever it occurs, irrespective of time elapsed since last dose of study drug.

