The median duration of TEAE (in days) will be calculated using Kaplan Meier analysis for all patients and AE included in a cluster. Unresolved AEs or AEs with missing resolution information and date will be treated as censored data with the end of extended on-treatment period as censoring date.

Death summary table will present reasons for deaths on treatment period, in survival follow-up, and overall.

Death details will also be listed (if applicable) including:

- Number of doses of balstilimab
- Number of cycles

- Age at death
- Study days relative to first dose date, calculated as (death date – first dose date + 1)
- Number of days to death from last dose, calculated as (death date – last dose date + 1)
- Precipitating AE (if death is an outcome of AE)
- Immune-related AE (if death is an outcome of irAE per investigator)
- Cause of deaths

The following listings will be provided in Safety Analysis Set:

- All AEs (with TEAEs flagged)
- Related TEAEs
- Serious TEAEs
- TEAEs leading to treatment discontinuation
- TEAEs leading to death
- Death details (including age, study day, and days from last dose, AEs, and death cause).

Adverse events observed between signing the informed consent and first dose of study drug will be listed with negative study days.

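### SAP 5.6 caps a partial AE resolution date at last dose + 90 days with no lower bound, so some AEs that ended later enter the duration summaries as resolved too early

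*SAP*

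**What the plan says.** SAP 5.6 sets the rule: "A partially missing resolution date will be conservatively imputed as the latest date in the range of missing date element(s) (for example 2020-10-31" is its first part and worked example. The sentence then lists the other candidates and the choice among them: "date of last dose + 90 days, day of study discontinuation, or death, whichever comes first". So the imputed date is the minimum of four dates.

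The only check in 5.6 on the order of onset and resolution concerns a missing onset: "If the resulting onset date is after a reported date of resolution, the onset date will be set equal to the date of resolution". It moves the onset. It sets no floor under an imputed resolution.

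SAP 5.4 ends the extended on-treatment period at the same horizon: "through 90 days after the last dose of study treatment or end of study, whichever occurs first". SAP 7.6.2 evaluates immune-related AEs and the immune-mediated clusters in that period. It reports a Kaplan-Meier median duration for each cluster and a median duration for the first instance of each irAE. In the Kaplan-Meier analysis, AEs that are unresolved or lack resolution information "will be treated as censored data with the end of extended on-treatment period as censoring date".

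The protocol follows AEs past that horizon. Section 6.3.3.2 follows Grade > 1 AEs until they improve to Grade 0-1 or a new therapy starts, and ongoing drug reactions until they resolve or stabilise. Section 7.3 follows ongoing SAEs to stabilisation or outcome. Once the Safety Follow-up Visit has taken place, Section 7.2.1 says that "only treatment-related AEs will be documented through the Treatment Follow-up Period of up to 12 months after the last dose of study drug", unless progression or a new therapy comes first.

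**The concern.** A rule that picks the latest possible date is conservative for duration, because it cannot understate how long an AE lasted. Taking the minimum with last dose + 90 days reverses this whenever the recorded month or year begins after the cap. The site has then stated that the AE was still present after the cap, and the analysis date contradicts that.

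Duration of TEAEs is a named Phase 2 secondary endpoint (Protocol 2.1.2, SAP 3.5). Slowly resolving immune-related events are the ones that can end after the cap. An AE of this kind is treated as shorter than an otherwise identical AE with a complete date. It also counts as a resolution at the point where an AE still unresolved would only be censored.

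**Working it through.** **Inputs.** The imputation rule is from SAP 5.6. The interval formula is from SAP 7.2: end date minus start date, plus 1 day. The documents contain no patient-level dates, so the last-dose and onset dates below are assumptions chosen for illustration.

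**Formula.** Imputed resolution = min(end of missing range, last dose + 90 days, study discontinuation, death).

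**The SAP's own example.** The entry is 2020-10-UNK. Assume last dose 1 September 2020 and no discontinuation or death before November. The cap is 30 November, so the minimum is 31 October 2020. This matches the SAP and shows that the rule works when the cap does not bind.

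**When the cap contradicts the entry.** For 2020-10-UNK this happens if last dose + 90 days falls before 1 October, that is, if the last dose was before 3 July 2020. A last dose on 1 July gives 29 September, which is outside October. A last dose on 20 July gives 18 October, which is earlier than the end of the month but still consistent with the entry.

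**Illustration.** Last dose 12 June 2020, so the cap is 10 September. Onset is 20 August, inside the extended on-treatment period. The entry is 2020-10-UNK, with no earlier discontinuation or death.

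| Information on resolution | Date used | Duration | Role in the cluster Kaplan-Meier analysis |
|---|---|---|---|
| 2020-10-UNK, SAP rule | 10 Sep | 21 + 1 = 22 days | resolved |
| 2020-10-UNK, earliest date the entry allows | 1 Oct | 42 + 1 = 43 days | resolved |
| 2020-10-UNK, latest date the entry allows | 31 Oct | 72 + 1 = 73 days | resolved |
| Complete date, 15 Oct | 15 Oct | 56 + 1 = 57 days | resolved |
| Unresolved | 10 Sep | 22 days | censored |

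The imputed duration is 22/43 = 51% of the shortest possible value and 22/73 = 30% of the longest, so it is 49% to 70% too short for this AE.

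**A second set of assumed dates.** Last dose 1 May 2020 (cap 30 July), onset 10 June, entry 2020-10-UNK. The SAP rule gives 51 days. The entry allows 114 to 144 days, and a complete date of 15 October would give 128.

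**The case against.** **The 90-day horizon is deliberate.** The cap matches the extended on-treatment period, and SAP 7.6.2 censors unresolved AEs at its end. This stands as a reason for having a horizon. It does not justify recording a resolution at the horizon for an AE known to have continued. An AE known only to outlast the window would be censored there. Nor does the SAP apply the horizon to complete dates.

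**Section 5.6 concerns TEAE status only.** It opens with "When determining TEAEs, partial dates will be handled as follows". But SAP 7.6.2 decides TEAE status from onset or worsening, so a cap on the resolution date has no evident role there. Its natural use is duration, and the SAP gives no other rule for a partial resolution date. For comparison, SAP 5.7 sets a partial medication stop date to the end of the known month or year with no such cap.

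**The size depends on chosen dates.** This stands. The first example starts 69 days after last dose, close to the cap, which makes the relative error large. An AE starting on or before last dose has at least 91 days to the cap. A median is unchanged if the shortened value still exceeds it. No shift in any cluster median is demonstrated.

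**Stronger readings a reader might infer.**

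- *Resolution before onset in the reported durations.* The formula can produce this: onset 150 days after last dose gives a resolution 60 days before onset. But such an onset lies outside the extended on-treatment period, so it reaches no cluster or irAE duration summary.
- *The record itself is changed.* It is not: "Data listings will present the partial date as recorded in the electronic case report form (eCRF", so only the analysis date moves.
- *Percent resolved is inflated.* A partial resolution date means the site reported resolution, so the AE counts as resolved on either date.

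**Conclusion.** The rule is wrong as written, in a narrow set of cases: AEs with onset inside the extended on-treatment period and a partial resolution date whose recorded month or year begins after last dose + 90 days. For each such AE, if no earlier death or discontinuation applies, the imputed date is earlier than any date consistent with the eCRF, and the duration is too short.

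This rests on the plain reading of 5.6 as a minimum of four dates and on its use for the durations in 7.6.2. The amounts for single AEs depend on the assumed dates. The number of affected AEs cannot be obtained from the documents and may be small, so the effect on any reported median is unknown. The primary ORR analysis does not use these dates. This is a minor point, worth correcting because the correction is cheap.

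**What to change.** Either of two changes is enough.

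1. In SAP 5.6, add that an imputed resolution date may not be earlier than the later of the AE onset date and the first day of the recorded month or year. Keep the existing caps otherwise, including study discontinuation and death. In the first illustration the imputed date becomes 1 October and the duration 43 days, the shortest value consistent with the entry.
2. If a 90-day horizon is intended for duration, say so in SAP 7.6.2. Censor at the end of the extended on-treatment period any AE whose earliest possible resolution is later, as is already done for unresolved AEs, and apply the same rule to complete dates. The illustrated AE then contributes 22 days, censored.

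Either change costs one sentence and a small change to the date program. Some AE durations become longer or censored.
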